Drug-Related Adverse Event (AE) per CTCAE V5	Severity	Action Taken	Clarifications, Exceptions, and Resume Criteria
Hepatic			
Aspartate aminotransferase (AST), alanine aminotransferase (ALT), or total bilirubin (T.bili) increased	AST or ALT > 3x and ≤ 5 x upper limit of normal (ULN) or T.Bili >1.5x and ≤ 3 x ULN, regardless of baseline value	Delay dose	Dosing may resume when laboratory values return to baseline.
	AST or ALT > 5 x ULN or T. bili > 3 x ULN, regardless of baseline value	Delay dose or Permanently discontinue	In most cases of AST or ALT > 5 x ULN, study treatment will be permanently discontinued. If the investigator determines a possible favorable benefit/risk ratio that warrants continuation of study treatment, a discussion between the investigator and the Medical Monitor/ designee must occur and a written agreement from Medical Monitor prior to resuming therapy.
	Concurrent AST or ALT > 3 x ULN and T.bili > 2 x ULN, regardless of baseline value	Permanently discontinue	
Endocrinopathy			
Adrenal Insufficiency	Grade 2 adrenal insufficiency	Delay dose	Dosing may resume with lab confirmation of hormone replacement treatment.
	Grade 3 or 4 adrenal insufficiency or adrenal crisis	Delay dose or permanently discontinue	Mandatory discussion with and approval from the Medical Monitor needed prior to resuming therapy. If adrenal insufficiency resolves or is adequately controlled with physiologic hormone replacement, participant may not require discontinuation of study drug.
Hyperglycemia	Hyperglycemia requiring initiation or change in daily management (Grade 2 or 3)	Delay dose	Dosing may resume if hyperglycemia resolves to Grade ≤ 1 or baseline value, or is adequately controlled with glucose-controlling agents.
	Grade 4	Delay dose or permanently discontinue	Mandatory discussion with and approval from the Medical Monitor needed prior to resuming therapy. If hyperglycemia resolves, or is adequately controlled with glucose-controlling agents, participant may not require discontinuation of study drug.

Drug-Related Adverse Event (AE) per CTCAE V5	Severity	Action Taken	Clarifications, Exceptions, and Resume Criteria
Hypophysitis/Hypopituitarism	Symptomatic Grade 1-3 that is also associated with corresponding abnormal lab and/or pituitary scan	Delay dose	Dosing may resume if endocrinopathy resolves to be asymptomatic, or is adequately controlled with only physiologic hormone replacement.

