6.6.1.4 Additional Safety Precautions (Advanced Prostate Cancer Cohort Only)

The safety profile for nivolumab (1 mg/kg) in combination with ipilimumab (3 mg/kg) is well established in melanoma and HCC at more frequent ipilimumab administration (Q3W vs Q6W) than proposed for this cohort ([Opdivo USPI, 2020](#)). Hence, concurrent enrollment will be pursued with participants allocated to regimens containing either ipilimumab 3 mg/kg or 5 mg/kg Q6W for up to 2 doses in combination with nivolumab 1 mg/kg. As the combination regimen with ipilimumab 5 mg/kg has not been extensively studied, in addition to adverse events being reviewed by the Sponsor on an ongoing basis and investigator meetings convening approximately every 2 weeks to discuss and review safety events, a safety pause is included.

Enrollment will pause until all participants have been followed for at least 6 weeks. During the pause, new participants may be consented and screened, but not initiated on study intervention. The safety pause will apply to both cohorts to preserve random allocation; however, the safety assessment as follows will apply to the ipilimumab 5 mg/kg cohort specifically. The initial 5 participants enrolled in the ipilimumab 5 mg/kg cohort will be observed for the occurrence of treatment-related adverse events (TRAEs) necessitating discontinuation of both agents (AEs requiring discontinuation are included in [Table 9](#)) from the beginning of treatment through completion of the first cycle (ie, 6 weeks).

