If 3 or fewer of the first 5 participants in the ipilimumab 5 mg/kg cohort (Prostate Cohort B) experience a TRAE leading to discontinuation of both agents, an additional 10 participants will be enrolled to receive nivolumab 1 mg/kg Q3W and ipilimumab 5 mg/kg Q6W for 2 cycles, then nivolumab maintenance 480 mg Q4W until PD or intolerable toxicity (Prostate Cohort B). If 4 or more of the first 5 participants of the ipilimumab 5 mg/kg cohort (Prostate Cohort B) experience a TRAE leading to discontinuation of both agents, an additional 10 participants will be enrolled to receive nivolumab 1 mg/kg Q3W and ipilimumab 3 mg/kg Q6W for 2 cycles, then nivolumab maintenance 480 mg Q4W until PD or intolerable toxicity (Prostate Cohort A). Only TRAEs leading to treatment discontinuation of both agents occurring up until the 5th participant in each cohort completes Cycle 1 will be included—dose delays for adverse events not otherwise meeting criteria at that time will not be counted. The stopping rule was chosen as this

corresponds to a > 80% chance that the toxicity rate in the cohort is > 40%, assuming a beta (0.8, 1.2) prior.

If either prostate cohort demonstrates 8 or greater TRAEs requiring discontinuation of therapy at any time, enrollment will be suspended until an ad hoc safety review convenes and provides a recommendation, as described above.

Table 9: Toxicity Criteria Requiring Permanent Treatment Discontinuation of Both Nivolumab and Ipilimumab (Amendment 3+ Advanced Prostate Cohort Only)

Participants should be monitored for the occurrence of any of the following AEs that are considered by the Investigator to be possibly, probably, or definitely related to ipilimumab, nivolumab, or the immunotherapy combination.
 
Treatment with all study intervention should be monitored for the occurrence of any of the following TRAEs, and if any of these events occur, action should be taken as follows:

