
• Any Grade 2 drug-related uveitis, eye pain or blurred vision that does not respond to topical therapy and does not improve to Grade 1 severity within the re-treatment period OR requires systemic treatment.• Any Grade 3 non-skin, drug-related AE lasting > 7 days, or recurs with the following exceptions for laboratory abnormalities, diarrhea, colitis, neurologic toxicity, drug-related uveitis, pneumonitis, bronchospasm, hypersensitivity reactions, infusion reactions, and endocrinopathies:
○ Grade 3 drug-related diarrhea, colitis, neurologic toxicity, uveitis, pneumonitis, bronchospasm, myocarditis, hypersensitivity reaction, or infusion reaction of any duration requires discontinuation.○ Grade 3 drug-related endocrinopathies, adequately controlled with only physiologic hormone replacement do not require discontinuation. Adrenal insufficiency requires discontinuation regardless of control with hormone replacement.○ Grade 3 drug-related laboratory abnormalities do not require treatment discontinuation except:
▪ Grade 3 drug-related thrombocytopenia > 7 days or associated with bleeding requires discontinuation.▪ Any drug-related liver function test abnormality that meets the following criteria require discontinuation:
• Grade ≥ 3 drug-related AST, ALT or total bilirubin requires discontinuation.
○ In most cases of Grade 3 AST, ALT evaluation study drug(s) will be permanently discontinued. If the investigator determines a possible favorable benefit/risk ratio that warrants continuation of study drug(s), a discussion between the investigator and the Medical Monitor (or designee) must occur.• Concurrent AST or ALT > 3x ULN and total bilirubin > 2x ULN.• Any Grade 4 drug-related adverse event or laboratory abnormality (including but not limited to creatinine, AST, ALT, or total bilirubin), except for the following events which do not require discontinuation:
○ Grade 4 neutropenia ≤ 7 days.○ Grade 4 lymphopenia or leukopenia or asymptomatic amylase or lipase.○ Isolated Grade 4 electrolyte imbalances/abnormalities that are not associated with clinical sequelae and are corrected with supplementation/appropriate management within 72 hours of their onset.○ Grade 4 drug-related endocrinopathy adverse events, such as, hyper- or hypothyroidism, or glucose intolerance, which resolve or are adequately controlled with physiologic hormone replacement (corticosteroids, thyroid hormones) or glucose-controlling agents, respectively, may not require discontinuation after discussion with and approval from the Medical Monitor (or designee).• Any event that leads to delay in dosing lasting > 12 weeks from the previous dose requires discontinuation, with the following exceptions:
○ Dosing delays to allow for prolonged steroid tapers to manage drug-related adverse events are allowed.

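### Table 9 makes controlled Grade 3 adrenal insufficiency a mandatory stop but, read in place, lets controlled Grade 4 adrenal insufficiency continue with Medical Monitor approval

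*Protocol*

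**What the plan says.** Section 6.6.1.1 of the Protocol sends the Amendment 3+ prostate cohorts to Table 9 for discontinuation requirements and keeps Table 7 for Amendments 1 and 2. Table 9 treats Grade 3 and Grade 4 events in separate bullets.

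- **Grade 3 bullet.** Most non-skin drug-related events that last more than 7 days or recur require stopping, with listed exceptions. The endocrinopathy exception spares Grade 3 events controlled by physiologic hormone replacement. The next sentence in the same sub-bullet adds: "Adrenal insufficiency requires discontinuation regardless of control with hormone replacement".
- **Grade 4 bullet.** Any drug-related Grade 4 event requires stopping, again with exceptions. One covers "Grade 4 drug-related endocrinopathy adverse events, such as, hyper- or hypothyroidism, or glucose intolerance, which resolve or are adequately controlled with physiologic hormone replacement". It gives corticosteroids and thyroid hormones as examples of replacement, and it adds glucose-controlling agents for glucose intolerance. These events "may not require discontinuation after discussion with and approval from the Medical Monitor".

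Table 7 (Section 6.6.1.1) puts Grade 3 and Grade 4 adrenal insufficiency in one row, requires Medical Monitor approval to resume, and says: "If adrenal insufficiency resolves or is adequately controlled with physiologic hormone replacement, participant may not require discontinuation of study drug".

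**The concern.** The adrenal sentence sits in the Grade 3 sub-bullet but carries no grade of its own. The Grade 4 exception is open-ended, because its examples are introduced by 'such as', and it does not exclude adrenal insufficiency. For a participant with Grade 4 adrenal insufficiency controlled on hormone replacement, the table does not say plainly whether treatment must stop.

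Table 9 is the mandatory stopping list for cohorts that include a regimen of which Section 6.6.1.4 says "the combination regimen with ipilimumab 5 mg/kg has not been extensively studied". A list of that kind should not be laxer at the higher grade, and it should not leave the Investigator and Medical Monitor to decide which line governs. Table 9 discontinuations also feed the early Cohort B safety assessment, which counts "Only TRAEs leading to treatment discontinuation of both agents".

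**Working it through.** This point rests on wording, so the check sets the lines of Table 9 side by side.

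**1. Outcome for an event controlled by hormone replacement, under each reading of the adrenal sentence**

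| Event | Sentence covers Grade 3 only (read in place) | Sentence covers all grades |
|---|---|---|
| Grade 3 endocrinopathy, not adrenal | May continue | May continue |
| Grade 3 adrenal insufficiency | Must stop | Must stop |
| Grade 4 endocrinopathy, not adrenal | May continue with approval | May continue with approval |
| Grade 4 adrenal insufficiency | May continue with approval | One line says stop; the other allows continuing with approval |

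The first reading gives a mandatory stop at Grade 3 and a discretionary continuation at Grade 4 for the same condition. The second gives two lines that pull in different directions at Grade 4.

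**2. Does placement settle the grade?** Not conclusively. The same Grade 3 branch contains liver items that reach beyond Grade 3: "Grade ≥ 3 drug-related AST, ALT or total bilirubin requires discontinuation" and, with no grade, "Concurrent AST or ALT > 3x ULN and total bilirubin > 2x ULN". Those items sit under their own header covering any drug-related liver test abnormality, so they set their own scope. They show only that position under the Grade 3 bullet is not decisive. They do not show that the adrenal sentence was meant for all grades.

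**3. Does the mention of corticosteroids settle it?** No. It makes it easy to read adrenal insufficiency into the Grade 4 exception. But Table 7 has a separate row for hypophysitis and hypopituitarism, also managed with physiologic hormone replacement, so the exception has other conditions to cover.

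**4. Does other text settle it?**
- Table 7 allows continuation at both grades, but Section 6.6.1.1 assigns it to Amendments 1 and 2.
- The last Table 9 bullet calls for stopping when the Investigator sees substantial clinical risk from continued nivolumab. That is a judgment clause and does not say which line governs.
- SAP Section 4.4 counts treatment-related events that force discontinuation of both agents, without defining them further.
- The endocrinopathy algorithm in Appendix 8 is a figure and could not be read for this check. Section 6.6 presents the algorithms as help in assessing and managing events.

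**5. The one nearby figure.** Section 6.6.1.4 says that 4 or more discontinuations in 5 correspond to a more than 80% chance that the toxicity rate exceeds 40%, under a beta(0.8, 1.2) prior. With x events in 5 the posterior is beta(0.8 + x, 1.2 + 5 − x).
- x = 3: Pr(rate > 0.40) under beta(3.8, 3.2) = 0.776, below 0.80.
- x = 4: Pr(rate > 0.40) under beta(4.8, 2.2) = 0.942, above 0.80.

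The stated boundary reproduces, and nothing here disturbs it. The link is only that Section 6.6.1.4 refers to Table 9 for the events to be counted.

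**The case against.** The strongest reply is that nothing in Table 9 contradicts anything else. Read in place, the adrenal sentence qualifies the Grade 3 exception and Grade 4 has its own bullet; two rules for two grades do not conflict. Read as all-grade, the line that names adrenal insufficiency would ordinarily prevail over a general class whose examples omit it. The Grade 4 default is to stop, the exception is permissive, stopping satisfies both lines on either reading, and every continuation passes through the Medical Monitor.

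Most of this stands, and it rules out three stronger readings that a reader might infer:
- *Table 9 flatly contradicts itself.* The documents do not establish this. A direct conflict needs the all-grade reading, which is possible but nowhere stated.
- *A controlled Grade 4 case would automatically continue.* It would not, because continuation needs discussion and approval.
- *The first-five Cohort B decision is compromised.* The documents give no rate for Grade 4 adrenal insufficiency, so neither a frequency nor a probability of changing that decision can be supported.

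The reply does not remove the inversion. The reading that avoids a contradiction is the one that makes the milder grade a mandatory stop and the more severe grade discretionary. Medical Monitor review limits the consequence, but the table does not tell the Medical Monitor whether that discretion extends to adrenal insufficiency.

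**Conclusion.** The point holds as a drafting defect in a mandatory safety table. In place, Table 9 is stricter for controlled Grade 3 than for controlled Grade 4 adrenal insufficiency; read as all-grade, its two lines conflict directly. The conclusion rests on two features of the text: the adrenal sentence states no grade, and the Grade 4 exception is open-ended without excluding the condition. Which reading was intended cannot be determined from the documents.

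The practical size is small and cannot be quantified. It concerns one condition at one grade, with a sponsor check already in place, and no analysis depends on it. It is a low-priority correction, worth making because it is simple and the table is binding.

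**What to change.** In the Grade 4 endocrinopathy exception of Table 9, add *except adrenal insufficiency*, followed by the requirement that the Grade 3 sub-bullet already states: stop regardless of hormone control. Adding no grade range avoids narrowing the existing sentence.

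The cost is one phrase at the next amendment, plus the Medical Monitor's discretion to continue a controlled Grade 4 case. No analysis or stated operating characteristic changes.

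The inconsistency could also be removed the other way, by adopting Table 7's rule for both grades. The stricter direction is preferred because Table 9 already requires stopping at Grade 3 despite hormone control, so the change extends an existing rule to the more severe grade. The limited experience with ipilimumab 5 mg/kg supports this for Cohort B only; Table 9 also covers the 3 mg/kg cohort. The phrase leaves open whether the ungraded sentence reaches Grade 2; if the sponsor wants that settled, the sentence itself should state its grades.

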6.7 INTERVENTION AFTER THE END OF THE STUDY

There will be no intervention following the end of the study.

7 DISCONTINUATIONS OF STUDY INTERVENTION AND PARTICIPANT DISCONTINUATION/WITHDRAWAL

7.1 DISCONTINUATION OF STUDY INTERVENTION

Participants must discontinue study intervention if they experience any of the following:

- Intolerable toxicity related to study intervention, including the development of an AE determined by the Investigator to be unacceptable even with the participant's potential response to intervention due to the severity of the event
- Any medical condition that may jeopardize participant safety if he or she continues the study intervention
- Use of another anticancer therapy
- Symptomatic deterioration attributed to disease progression that per assessment by the Investigator necessitates discontinuation of study intervention.
- Radiographic disease progression per RECIST v1.1, unless the participant in the nivolumab monotherapy arm decides to enroll into the nivolumab and ipilimumab combination treatment arm (see [Appendix 3](#)). Refer to [Section 4.4](#) for description of treatment beyond progression.
- Pregnancy (see [Appendix 6](#))

Participants have the right to voluntarily withdraw from study intervention at any time for any reason. In addition, the Investigator has the right to withdraw a participant from study intervention at any time. Reasons for withdrawal from study intervention may include, but are not limited to, the following:

- Investigator or Sponsor determines it is in the best interest of the participant

- Participant noncompliance

The primary reason for study intervention discontinuation should be documented on the appropriate electronic case report form (eCRF) page.

The visit at which disease assessment shows PD may be used as the end of treatment visit. Participants who discontinue study intervention for any reason other than PD or loss of clinical benefit are to continue assessments as outlined in the Schedule of Activities (SOAs; see [Section 1.3](#)).

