1.3 SCHEDULE OF ACTIVITIES

The Schedule of Activities (SOAs) for the nivolumab only arm and nivolumab plus ipilimumab combination arm are shown in [Table 1](#) and [Table 2](#) for advanced metastatic cancer and in [Table 3](#) and [Table 4](#) for advanced prostate cancer.

Table 1: Schedule of Assessments Advanced Metastatic Cancer (Nivolumab Only Arm: Nivolumab 360 mg Q3W and Maintenance 480 mg Q4W)

Tests & Procedures	Screening ^a	On-Treatment Evaluations									End of Treatment	Follow up ^b	
		C1		C2	C3	C4	C5	C6	C7	C8		15-30 days after last dose	First visit (90 days after last dose) ^b
Day	0	D1	D8	D1	D1	D1	D1	D1	D1	D1			
Window (days)	-28 to 0	--	± 3	± 3	± 3	± 3	± 3	± 3	± 3	± 3	± 7	± 7	± 7
Informed consent ^a	X												
Medical, cancer history ^d	X												
Physical examination	X			X	X	X	X	X	X	X	X	X	
Pregnancy test (serum or urine) ^e	X ^e			X	X	X	X	X	X	X	X		
ECOG performance status	X			X	X	X	X	X	X	X	X	X	
Vital signs (see Section 8.2.3) ^f	X	X		X	X	X	X	X	X	X	X	X	
Body weight	X	X		X	X	X	X	X	X	X			
Hematology (see Table 10)	X		X	X	X	X	X	X	X	X	X	X	
Clinical chemistry (see Table 10)	X		X	X	X	X	X	X	X	X	X	X	
Urinalysis	X		X	X	X	X	X	X	X	X	X	X	
12-lead ECG	X												
Tumor markers ^g	X			X	X	X	X	X	X	X	X		
cfDNA (blood) ^h	X			X							X		
Circulating soluble analytes ⁱ	X	X	X	X	X	X					X		
Blood immune biomarkers ⁱ	X	X	X	X	X	X					X		
Stool collection ^j	X			X									
Tumor biopsy ^k	X ^l	As early as possible after the 2nd dose of nivolumab monotherapy ^k and at PD											
Concomitant medications ^m	X	X	X	X	X	X	X	X	X	X	X	X	
Adverse events ^m	X	X	X	X	X	X	X	X	X	X	X	X	
Nivolumab administration ⁿ		X		X	X	X	X ^o	X	X	X			
Follow-up for overall survival ^c												X	X

Tests & Procedures	Screening ^a	On-Treatment Evaluations									End of Treatment	Follow up ^b	
		C1		C2	C3	C4	C5	C6	C7	C8		15-30 days after last dose	First visit (90 days after last dose) ^b
Day	0	D1	D8	D1	D1	D1	D1	D1	D1	D1			
Window (days)	-28 to 0	--	± 3	± 3	± 3	± 3	± 3	± 3	± 3	± 3	± 7	± 7	± 7
Assess subsequent cancer therapy											X	X	X
Disease assessment ^d	X	Cycle 4 Day 1, then beginning at Cycle 6 Day 1, repeat every 8 weeks (± 7 days) until radiographic progression or the start of subsequent therapy, whichever comes first											

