3 OBJECTIVES AND ENDPOINTS

The study objectives and endpoints are listed in [Table 5](#).

Table 5: Objectives and Corresponding Endpoints

Objectives	Endpoints
Primary	

 To determine the clinical benefit rate (CBR) of nivolumab with or without ipilimumab in participants with advanced metastatic cancer, including advanced prostate cancer. To assess the proportion of participants in the nivolumab plus ipilimumab arm whose tumors will change from CD8 low to CD8 high as measured by a change in the percentage of tumoral CD8 cells. 	
 CBR is the proportion of participants who show clinical benefit, defined as CR, PR, or SD for ≥ 6 months as best response by RECIST v1.1. Change in the percentage of CD8 cells in on-treatment biopsies from baseline.
Secondary	

 To determine the safety and tolerability of nivolumab with or without ipilimumab in participants with advanced metastatic cancer, including advanced prostate cancer. To determine the ORR of nivolumab with or without ipilimumab in participants with advanced metastatic cancer, including advanced prostate cancer. To assess the association of percentage of CD8 infiltration in tumor samples with clinical outcomes (ORR, PFS, and OS). 	
 Incidence and severity of AEs based on CTCAE v5.0. ORR: Defined as CR or PR as best response by RECIST v1.1 assessment. PFS: Defined as the time from initiation of study therapy to date of first documented progression of disease or date of death due to any cause. OS: Defined as the time from initiation of study therapy until death due to any cause.
Exploratory	

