7.2 PARTICIPANT DISCONTINUATION/WITHDRAWAL FROM STUDY

When study intervention is discontinued, participants should have an end of treatment/discontinuation assessment and continue follow-up assessments until radiographic progression or the start of subsequent therapy, whichever comes first, as outlined in the SOAs (see [Section 1.3](#)). In addition, ad hoc scans, as part of standard of care, will be collected for participants who have discontinued treatment for reasons other than radiographic progression and prior to any alternate therapies. Information on survival follow-up and new anticancer therapy will be collected for all participants via telephone calls, participant medical records, and/or clinic visits, until any of the following occurs:

- Death
- Lost to follow-up
- Study termination by the Sponsor
- Participant requests to be withdrawn from follow-up
- Investigator requests that the participant is withdrawn from follow-up

If a participant requests to be withdrawn from the study, the request must be documented in the source documents and signed by the Investigator. The primary reason for withdrawal from study should be documented on the appropriate eCRF page. If the participant withdraws from study, the Sponsor may retain and continue to use any data collected before such withdrawal of consent. In addition, the study staff may use a public information source (eg, county records) to obtain information about survival status only. However, participants who withdraw consent will not be followed for any reason after consent has been withdrawn. Participants who receive study intervention and subsequently withdraw from the study will not be replaced.

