8.1 EFFICACY ASSESSMENTS

Participants will undergo tumor assessments as designated in the SOAs (see [Section 1.3](#)) regardless of dose delays, until loss of clinical benefit as determined by the Investigator (unless the participant withdraws consent or the Sponsor terminates the study). All participants who discontinue study intervention for reasons other than radiographic progression (eg, AEs) will continue tumor assessments until death, disease progression, initiation of another systemic anticancer therapy, loss to follow-up, withdrawal of consent, or study termination, whichever occurs first. At the Investigator's discretion, tumor assessments may be repeated at any time if PD is suspected.

Measurable and evaluable lesions should be assessed and documented at screening. Tumor assessments performed as standard of care prior to obtaining informed consent and within 28 days prior to treatment do not have to be repeated at screening.

Screening assessments must include computed tomography (CT) scans (with IV contrast unless contraindicated and oral contrast as appropriate per institutional standards). A spiral CT scan of the chest may be obtained but is not a requirement. If a CT scan with contrast is contraindicated (ie, in participants with contrast allergy or impaired renal clearance), a non-contrast CT scan of the chest may be performed and magnetic resonance imaging (MRI) scans of the abdomen, pelvis, and head (as applicable) should be performed as applicable.

If a CT scan for a tumor assessment is performed in a positron emission tomography (PET)/CT scanner, the CT acquisition must be consistent with the standards for a full contrast diagnostic CT scan.

Bone scans (technetium-99m [TC-99m]) or sodium fluoride (NaF) PET should be performed at screening if clinically indicated. If bone metastases are present at screening and cannot be seen on CT or MRI scans, or if clinically indicated, TC-99m and NaF-PET bone scans should be repeated when complete response (CR) is identified in target disease or when progression in bone is suspected.

CT scans of the head, neck, or extremities should also be performed if clinically indicated and repeated throughout the study if there is evidence of disease at screening.

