##### 5.4.2.2 Progression-Free Survival

Progression-Free Survival (PFS) is defined as the time from initiation of study intervention to the date of first documented radiographic progression of disease or date of death due to any cause, whichever occurs first. Participants who continue treatment beyond initial disease progression will be considered to have progression of disease (PD) at the time of the initial progression event.

Participants who do not have radiographic PD at the time of analysis will be censored as follows:

- Participants who do not have radiographic PD and are still on study at the time of analysis will be censored at the date of the last tumor assessment documenting absence of progressive disease.
- Participants who have discontinued study treatment and have started subsequent anti-cancer therapy or had subsequent cancer surgery or radiation prior to documentation of radiographic PD will be censored at the date of the last evaluable tumor assessment prior to the initiation of subsequent treatment.

- Participants who discontinued the study prior to documentation of radiographic PD will be censored at the date of the last tumor assessment documenting absence of progressive disease.
- Participants who do not have radiographic PD and who die more than 16 weeks from their last evaluable tumor assessment will be censored at the date of the last tumor assessment documenting absence of progressive disease. Participants who die within 16 weeks of their last evaluable tumor assessment will be considered as having an event at the date of death.

PFS will be estimated using Kaplan-Meier techniques, and the median survival time and 95% CIs will be estimated within each study intervention group.

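### The protocol gives two rules for when scans stop after clinical deterioration; under the Section 7.1 rule, SAP censoring biases PFS upward by an amount that is probably small and is not addressed in the plan

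*Protocol*

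**What the plan says.** On when tumor assessments stop, the protocol speaks with two voices.

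- **Ending at loss of clinical benefit.** Section 7.1: "Participants who discontinue study intervention for any reason other than PD or loss of clinical benefit are to continue assessments". Those excepted are, by implication, not required to continue. The first sentence of Section 8.1 is direct: tumor assessments run "regardless of dose delays, until loss of clinical benefit as determined by the Investigator".
- **Continuing past it.** Section 7.2 has participants who stop treatment "continue follow-up assessments until radiographic progression or the start of subsequent therapy, whichever comes first". The second sentence of 8.1: "All participants who discontinue study intervention for reasons other than radiographic progression (eg, AEs) will continue tumor assessments until death", or another listed end such as progression or new systemic therapy. The schedules in Section 1.3 have no exception for loss of benefit; for example, "repeat every 8 weeks (± 7 days) until radiographic progression or the start of subsequent therapy, whichever comes first".

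Section 7.1 also makes the affected situation a required reason to stop treatment: "Symptomatic deterioration attributed to disease progression that per assessment by the Investigator necessitates discontinuation of study intervention".

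The protocol (Section 3) defines PFS to the "date of first documented progression of disease or date of death due to any cause". SAP 5.4.2.2 narrows progression to radiographic progression and censors, at the last scan, anyone without it who is still on study, has left the study or has started new therapy. It adds: "Participants who do not have radiographic PD and who die more than 16 weeks from their last evaluable tumor assessment will be censored". A death within 16 weeks of the last evaluable scan is an event at the date of death. SAP Section 6, which lists departures from the protocol, mentions neither the radiographic restriction nor the 16-week rule.

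**The concern.** A site with a participant who deteriorates clinically without radiographic PD cannot satisfy all of these sections. If it follows 7.1 and the opening of 8.1, scanning stops because the participant is getting worse. The SAP then treats that participant as progression-free up to the last scan and as uninformatively censored afterwards. Kaplan-Meier assumes that those censored have the same future risk as those still followed; here their risk is higher, so the PFS curve sits too high. A death more than 16 weeks after the last scan is also lost, although the endpoint includes death from any cause. The affected result is a secondary endpoint reported for each intervention group as a median with a 95% CI.

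**Working it through.** **No plan figure to reproduce.** The documents give no PFS median, event count or rate of clinical-only progression. The check therefore has two parts: how the rules interact, and an illustration of size under stated assumptions.

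**How the rules interact.** In the nivolumab-only schedule, Cycle 4 Day 1 is week 3 × 3 = 9 and Cycle 6 Day 1 is week 4 × 3 + 4 = 16; scans follow every 8 weeks. Take a participant whose last scan is at week 16 and who then deteriorates without radiographic PD or new therapy.

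- Scans stop (7.1): a death up to week 16 + 16 = 32 is an event at the date of death. Any later death is discarded and the participant is censored at week 16.
- Scans continue (7.2 and the schedules): scans fall at weeks 24, 32 and so on. Either one shows PD, or a death comes about 8 weeks or less after the last scan (plus the 7-day window) and counts.

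The 16-week limit is 2 × 8 weeks. It works as a missed-scan rule when scanning continues. It discards deaths systematically only when scanning is stopped by design.

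**No post-baseline scan.** Section 8.1 accepts a screening scan up to 28 days (4 weeks) before treatment. The SAP does not say whether that scan counts as the last evaluable assessment. If it does, the window can close at week 16 − 4 = 12 after first dose. A death at week 13 is then 13 + 4 = 17 weeks from the scan and would be censored at the scan date, at or before time zero.

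**Illustration of size.** The simulation used 200,000 participants per scenario, with scans at weeks 9, 16 and every 8 weeks after. Assumptions not in the documents:

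- exponential time to progression, median 3 or 5 months;
- exponential survival after progression, median 1.5, 3, 6 or 12 months;
- 5%, 10% or 20% of progressions clinical only;
- 0% or 30% of clinical-only progressors starting new therapy, which censors them under either scan rule;
- no deaths before progression;
- with continued scanning, PD is seen at the next scheduled scan (a later appearance would narrow the gap);
- with no post-baseline scan, the 16 weeks run from first dose.

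That makes 2 × 4 × 3 × 2 = 48 scenarios. The rise is 6-month PFS with scans stopped and the SAP rule applied, minus 6-month PFS with scans continued:

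| Clinical only | Smallest rise (points) | Largest rise (points) |
|---|---|---|
| 5% | 47.1 − 46.7 = 0.4 | 47.7 − 46.3 = 1.4 |
| 10% | 29.3 − 28.5 = 0.8 | 49.5 − 46.7 = 2.8 |
| 20% | 31.4 − 29.7 = 1.7 | 52.6 − 46.6 = 6.0 |

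The smallest rises come with 1.5-month survival after progression and 30% starting new therapy. The largest come with 12-month survival and none starting new therapy.

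**Median.** Most events fall on scan dates, so the curve drops in steps and the median tends to stay on a scan week (16 weeks, 3.7 months; or 24 weeks, 5.5 months). It is unchanged in every 5% and 10% scenario and in every 3-month scenario. It moves in 7 of 48, all at 5-month median and 20% clinical only, from 5.5 to between 5.8 and 7.4 months.

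**Deaths.** Across scenarios, about 10% to 72% of clinical-only progressors still count as events because they die within 16 weeks of the last scan.

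**What aligning the scan text leaves behind.** At 20% clinical only with 30% of them starting new therapy, 6-month PFS with scans continued is still 2.3 to 2.5 points above an analysis that dates clinical progression as an event. With none starting new therapy the gap is 0.5 to 0.6 points. Most of the remainder is therefore censoring at subsequent therapy, which applies under either scan rule.

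**The case against.** The best case on the other side has several parts.

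- Section 7.1 never orders scans to stop; it only lists who must continue. Section 7.2 and the schedules require the scans, and if sites follow those most of the bias does not arise. This limits the size, but the first sentence of 8.1 is explicit and the conflict remains.
- Radiographic progression is a reasonable choice for an open-label, investigator-assessed endpoint, and 16 weeks is a coherent missed-scan limit. This stands, and is why the primary PFS rule should be kept.
- The planned summary is the median, which rarely moves, and no 6-month PFS estimate is planned. This stands, although the curves are estimated too.
- Protocol Section 10.5.5, in the setting of adverse event recording, describes progression judged by symptoms as rare and asks for objective documentation. It is the only statement on frequency, so 20% is a pessimistic input. Inclusion criterion 8, however, admits non-prostate participants without RECIST-measurable disease, in whom radiographic PD may be harder to document.
- Sampling error is larger. With the planned 40 and 160 participants and PFS near 28%, the 95% half-width is 1.96 × √(0.28 × 0.72 / 40) = 0.139 and 1.96 × √(0.28 × 0.72 / 160) = 0.070, about 14 and 7 points. True, but the bias always goes one way and the interval does not reflect it.
- PFS is secondary and descriptive, SAP 5.4 disclaims hypothesis testing, no stopping rule uses PFS, and SAP Table 3 has no PFS model. This stands and bounds the consequence.

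A reader might infer that all later deaths of these participants are censored. The SAP does not say so: deaths within 16 weeks of the last evaluable scan are events. Dropping every such death would put the rise at 20% clinical only at about 5 to 7 points, rather than 1.7 to 6.0.

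**Conclusion.** The contradiction over when scans stop is real: 7.1 and the first sentence of 8.1 stand on one side; 7.2, the second sentence of 8.1 and the schedules on the other. Where sites follow the first, SAP 5.4.2.2 produces informative censoring and an upward bias in Kaplan-Meier PFS. The direction follows from the rules and held in all 48 scenarios. The size rests on an assumed rate of clinical-only progression and on the other assumptions listed above; at the lower rates that the protocol's own wording suggests, it is on the order of 1 point at 6 months with no change in the median.

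A reader might go further and conclude that reported PFS will be materially inflated, or that the primary result is affected. The documents do not support either. They give no rate from which material inflation could be derived. For CBR, SAP 5.4.1 does not count stable disease as benefit when its last assessment falls before 6 months, so stopping scans early cannot inflate it this way.

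This should be corrected because the text conflicts and the remedy is cheap. It does not threaten the trial's main conclusions.

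**What to change.** 1. **Protocol 7.1 and 8.1, first sentence.** Reconcile with 7.2, the second sentence of 8.1 and the schedules, so that loss of clinical benefit without radiographic PD does not end scheduled scans before subsequent therapy. This concerns assessments only; the criteria for stopping treatment are untouched.
2. **SAP 5.4.2.2, sensitivity analysis.** Keep the primary rule. Add one analysis that counts every death, and discontinuation for symptomatic deterioration, as events. It also shows how much the primary result depends on censoring at subsequent therapy, which item 1 does not remove.
3. **SAP 5.4.2.2, no post-baseline scan.** State that the 16 weeks then run from first dose.
4. **SAP Section 6.** List the radiographic-only definition and the 16-week rule as differences from the protocol.

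The cost is wording and one table. The scans are already required by 7.2, 8.1 and the schedules. The reason for stopping treatment is recorded on the eCRF (7.1), and survival is followed every 3 months for up to 2 years after the last dose (1.3), so no new data are needed.
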